### 9.2.3.5. Cohort 2: Summary of PK Sampling

A summary of the PK sampling scheduled in Cohort 2 is shown in **Table 5** below:

**Table 5:** Blood sampling schedule for pharmacokinetic assessments for Cohort 2

Study Visit	Dose of DTG	PK Sampling
Entry	1 st DTG dose (<7 days of life)	pre-, 1-3 hrs post-dose
Visit 2/3	Any time from 3 rd DTG dose but before Week 4 of life	pre-, 1, 2, 4, 6, 24-72* hrs post-dose
Visit 5	Any DTG dose in Week 4 of life	pre-dose, 1-3 hrs post-dose

*\*Depends on DTG dosing schedule*

The blood sampling has been designed to ensure blood volume limitation are in alignment with the SU HREC guideline for paediatric blood volumes for research purposes (Section 13.7)

### 9.3. Schedule of Evaluations

**Table 6.** Schedule of evaluations for Stage 1 Cohort 1A (n=8): Single dose of DTG in neonates in week 3 and 4 of life

Evaluation	Screening and Entry Visit(s) a	PK Visit 1a	PK Visit 1b	Safety Visit 1	Safety Phone Call
Visit windows	< 14 days of life	≥ 14 days and less than 28 days of life	24-30 hours post single DTG dose	1 week after PK Visit 1a (+/-4 days)	2 weeks after PK Visit 1a (+/-4 days)
Clinical					
Informed Consent	X				
History	X	X	X	X	X
Physical examination b	X	X		X	
Dispense DTG		X			
Acceptability questionnaire		X			
Laboratory					
Haematology c	X (0.5 mL)			X (0.5 mL)	
Chemistry d	X (0.8 mL)			X (0.8 mL)	
HIV-1 NAT Test e	X (0.8 mL)			X (0.8 mL)	
Pharmacology					
PK Blood Sampling f		X (2mL)	X (0.4mL)		
Total blood volume	2.1 mL	2 mL	0.4 mL	2.1 mL	

a Screening and entry procedures may be performed as one or 2 separate visit(s). All study required results should be available before entry with the exception of the HIV-1 NAT result which may be pending at time of study entry; b Physical and medical assessment includes length, weight, head measurements and monitoring of vital signs; c Haemoglobin, white blood cell count and differential, and platelets; d Creatinine, ALT, AST, total and direct bilirubin; e If HIV-1 NAT Test comes back positive, the HIV-infected neonate will be taken off study and initiated on standard of care HIV-treatment, as per local guidelines; f PK blood sampling at PK Visit 1a/b will occur at 1, 2, 3, 4, 6 and 24-30 hours post DTG single dose. Mothers and their neonates will return home after PK Visit 1a sampling time-points (1, 2, 3, 4 and 6 hours) and attend the following day for PK Visit 1b to complete the 24-30 hour PK sampling procedure. Laboratory tests may be repeated during the screening period dependent on specified blood draw limits.

**Table 7.** Schedule of evaluations for Stage 1 Cohort 1B (n=8): Single dose of DTG in neonates in week 1 and 2 of life

Evaluation	Screening and Entry Visit(s) a	PK Visit 1a	PK Visit 1b	Safety Visit 1	Safety Phone Call
Visit windows	≤3 days of life	<14 days of life	24-72 hours post single DTG dose	1 week after PK Visit 1a (+/-4 days)	2 weeks after PK Visit 1a (+/-4 days)
Clinical					
Informed Consent	X				
History	X	X	X	X	X
Physical examination b	X	X		X	
Dispense Study Drug		X			
Acceptability questionnaire		X			
Laboratory					
Haematology c	X (0.5 mL)			X (0.5 mL)	
Chemistry d	X (0.8 mL)			X (0.8 mL)	
HIV-1 NAT Test e	X (0.8 mL)			X (0.8 mL)	
Pharmacology					
PK Blood Sampling f		X (2 mL)	X (0.4 mL)		
Total blood volume	2.1 mL	2 mL	0.4 mL	2.1 mL	

a Screening and entry procedures may be performed as one or 2 separate visit(s). All study required results should be available before entry with the exception of the HIV-1 NAT result which may be pending at time of study entry; b Physical and medical assessment includes length, weight, head measurements and monitoring of vital signs; c Haemoglobin, white blood cell count and differential, and platelets; d Creatinine, ALT, AST, total and direct bilirubin; e If HIV-1 NAT Test comes back positive, the HIV-infected neonate will be taken off study and initiated on standard of care HIV-treatment, as per local guidelines; f PK blood sampling will occur at the following time points: pre-dose and 1, 2, 4, 6 and 24-72 hours post dose. Mothers and their neonates will return home after PK Visit 1a and attend 24–72 hours later (as applicable) for PK Visit 1b. Laboratory tests may be repeated during the screening period dependent on specified blood draw limits.

**Table 8.** Schedule of evaluations for Stage 2 Cohort 2 (n=24): Multiple doses of DTG in neonates commencing within 72 hours of life

Evaluation	Screening and Entry Visit(s) a	Visit 2	Visit 3	Visit 4	Visit 5	Safety Phone Call
Visit windows	< 7 days of life	Any time from 3 rd DTG dose but before Week 4 of life b	24 to 72 hours post Visit 2 DTG dose	1 week after Visit 2 (+/- 4 days) c	Week 4 of life (Day 22 – 28 of life)	2 weeks after Visit 5 (+/-4 days)
Clinical						
Informed Consent	X					
History	X	X	X	X	X	X
Physical examination d	X	X		X	X	
Dispense Study Drug e	X	X	X	X	X	
Acceptability questionnaire	X	X		X	X	
Adherence assessments		X		X	X	
Laboratory						
Haematology f	X (0.5 mL)			X (0.5 mL)		
Chemistry g	X (0.8 mL)	X (0.8 mL)		X (0.8 mL)	X (0.8mL)	
HIV-1 NAT Test f	X (0.8 mL)				X (0.8 mL)	
Pharmacology						
PK Sampling i	X (0.8 mL)	X (2.0 mL)	X (0.4 mL)		X (0.8mL)	
Total blood volume	2.9 mL	2.8 mL	0.4 mL	1.3 mL	2.4 mL	

a Screening and entry procedures may be performed as one or 2 separate visit(s). All study required results should be available before entry with the exception of the HIV-1 NAT result which may be pending at time of study entry; b Visit 2 and 3 should be scheduled any time from 3rd DTG dose but before week 4 of life; c Visit 4 can be conducted on the same day as Visit 5 but only if both falls within week 4 of life; d Physical and medical assessment includes length, weight, head measurements and monitoring of vital signs vital signs; e 1st DTG dose administered <7 days. The timing of the next dose of DTG and subsequent DTG doses will be determined using data from Cohort 1A and 1B. DTG will be administered until the neonate is 28 days old; f Haemoglobin, white blood cell count and differential, and platelets; g Creatinine, ALT, AST, total and direct bilirubin; h If HIV-1 NAT Test comes back positive, the HIV-infected neonate will be taken off study and initiated on standard of care HIV-treatment, as per local guidelines; i For the 1st DTG dose (PK: pre-dose sample and 1 more sample 1-3 hours post-dose); Any time from 3rd DTG dose but before week 4 of life (PK: pre-dose and 1, 2, 4, 6 and 24-72 hours post dose); For any DTG dose in Week 4 of life (PK: pre-dose sample and another sample 1-3 hours post-dose). Laboratory tests **may not** be repeated during the screening period as this will exceed blood draw limits.

## 9.4. Rescheduling, Deferment or Termination of PK Sampling

### Stage 1: Cohorts 1A and 1B

The PK blood sampling will be terminated if:

- Emesis occurs within 30 minutes of study drug administration for which the study team deem that the study drug administration has not been completely retained.
- If either the first or second PK sample at 1 or 2 hours post-dose are missed.

If the PK sampling is terminated the child will continue in the study for safety assessment but repeat PK sampling will not be performed. Participants who do not complete the PK visit in Stage 1 will be replaced.

### Cohort 2

The PK visit will be deferred at Visit 2 if the mother/caregiver reports their baby missing any of the previous 3 scheduled doses. In this event, the subject will be asked to continue on their current dosing, and if adherence is confirmed for 3 consecutive doses the PK visit can be performed.

Once started, the PK blood sampling at Visit 2 will be terminated if:

- Emesis occurs within 30 minutes of study drug administration for which the study team deem that the study drug administration has not been completely retained.

The PK blood sampling at Visit 2 may be rescheduled if it remains within the study visit window and the maximum blood volume drawn does not exceed the amount allowed. If it is not possible to complete the PK sampling at visit 2, the child will continue in the study and complete the remaining visits per protocol. Participants who do not complete the PK sampling at Visit 2 will be replaced.

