It is unknown the extent to which the DTG exposure will be increased as the enzyme pathways involved in DTG metabolism (UGT1A1 and CYP3A) mature at different rates during early life (30, 31). As expected, the washout elimination of DTG in neonates after *in utero* exposure was slow, with a median elimination half-life of 32.8 hours compared to 12-14 hours in children and adults. In this context, physiologically based pharmacokinetic (PBPK) modelling (32) has been utilized to predict DTG PK and dose optimization in neonates (33). This PBPK model combined existing knowledge on the anatomical, physiological, and metabolic changes (i.e., ontogeny of CYP3A4 and UGT1A1) in neonates with available physicochemical and *in-vitro* data of DTG. This PBPK model was validated using observed clinical data for RAL and midazolam in neonates. Using the final PBPK model, multiple DTG dose strategies were simulated in 100 healthy term virtual neonates (weight ranging from 3.0 to 4.5 kg) with the goal of achieving therapeutic DTG plasma  $AUC_{0-24}$  (50.1  $\mu\text{g}\cdot\text{h}/\text{mL}$ ) and trough concentration (0.99  $\mu\text{g}/\text{mL}$ ) observed in children. **The model predictions indicated that a 5 mg DTG dose may be suitable for term neonates, but any regimen would likely require increased dosing intervals during early life compared to older infants (e.g., every 48 or 72 hours compared to every 24 hours).** The authors' preferred regimen was 5 mg DTG doses every 48 hours from Day 1–20 of life, increasing to 5 mg once daily on Day 21. An important caveat of this PBPK model was the absence of maternal transfer of DTG through the placenta or breast milk. It has been shown that DTG readily crosses the placenta with a reported cord blood to maternal plasma ratio of 1.25 (1.07–1.40) (34). Breastfeeding has been reported to contribute relatively little to infant plasma exposure in the DolPHIN-1 study. The relative infant dose to that of the mother was estimated to be 0.27% (range, 0.13%–0.71%;  $n = 26$ ) (35).

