### 9.2.1.1. Cohort 1A: PK Visit 1a/1b

After study entry, PK Visit 1a and 1b for the neonate will be scheduled at **≥14 days and <28 days of life**. On the morning of the PK visit 1a, study nurses and physicians will take a medical history and examine the neonate. Afterwards, a single 5 mg dose of DTG (half of the 10 mg DTG-DT) will be administered. The study team will support the preparation and administration of the DTG-DT mixed with water with the parent(s) or caregiver/legal guardian and document the exact time of intake used for administration. Acceptability testing of the DTG-DT will be performed.

Following an observed dose, blood will be drawn at 1, 2, 3, 4, 6 (PK Visit 1a) and 24-30-hours (PK Visit 1b) post-dose. A blood draw window of +/- 15 minutes is acceptable for samples up to 6 hours post-dose. The last samples can be drawn anytime between 24 and 30-hours post-dose. It is planned to draw 0.4 mL per time point - a total blood volume of 2.4 mL for PK assessment. A short intravenous catheter (heparin lock) can be used to reduce repeated skin puncture and ease the discomfort of blood sampling.

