### 9.2.2. Stage 1: Cohort 1B

The screening and entry visit(s) will take place within ≤3 days of life. Screening and entry procedures may be performed as one or 2 separate visit(s). HIV-exposed neonates enrolled in Cohort 1B will continue to receive ARV prophylaxis as per local guidelines for the duration of the study.

If an HIV NAT test result comes back positive for a neonate at any time during the study, the neonate will not receive any further study drugs, come off study and will be treated as per standard of care (any prior PK samples will be included in the analysis).

At the end of study follow-up, HIV negative infants will continue standard of care HIV prophylaxis, if indicated, as per local guidelines.

### 9.2.2.1. Cohort 1B: PK Visit 1

After study entry, PK visit 1a and 1b for the neonate will be scheduled at **< 14 days of life**. On the morning of the PK visit, study nurses and physicians will take a medical history and examine the neonate. Afterwards, a single 5 mg dose of DTG (half of the 10 mg DTG-DT) will be administered. The study team will support the preparation and administration of the DTG-DT mixed with water with the mother and document the exact time of intake used for administration. Acceptability testing of the DTG-DT will be performed.

Blood will be drawn pre-dose, and then following an observed dose, at 1, 2, 4, and 6 (PK Visit 1a), and 24-72 hours (PK Visit 1b) post-dose. A blood draw window of +/- 15 minutes is acceptable for samples up to 6 hours post-dose. The last sample can be drawn anytime between 24 and 72-hours post-dose. It is planned to draw 0.4 mL per time point - a total blood volume of 2.4 mL for PK assessment. A short intravenous catheter (heparin lock) can be used to reduce repeated skin puncture and ease the discomfort of blood sampling.

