### 12.2.4. Pharmacokinetic Analysis

In Cohort 1, a non-compartmental pharmacokinetic analysis will be performed to calculate the PK parameters using Phoenix WinNonLin (Certara, USA). The following PK parameters will be determined:  $C_{max}$ ,  $T_{max}$ ,  $C_{24}$ ,  $AUC_{0-24}$ ,  $AUC_{0-infinity}$ , and Ratio  $AUC_{0-24}/AUC_{0-infinity}$ .  $C_{max}$ ,  $C_{last}$  and  $T_{max}$  will be taken directly from the observed concentration-time data.  $AUC_{0-all}$  and  $AUC_{0-inf}$  will be determined using the linear-up log-down trapezoidal method. Total body clearance for extravascular administration will be calculated using  $Dose/AUC_{0-infinity}$ . Median (range), means (standard deviations), and geometric means with 95%CI for each PK parameter will be calculated separately for Cohorts 1A and 1B, as well as for Cohort 1A/1B together.

Pharmacokinetic modelling and simulation analyses using all Stage 1 PK data will be performed to select the multi-dose schedule of 5 mg DTG for Cohort 2. Using appropriate PK models the DTG concentration time profiles will be simulated for different DTG dosing schedules (**Table 4**) and the  $C_{24}$  and  $C_{max}$  estimated. The DTG dosing schedule which best fits the PK target criteria (Section 11.4.1) will be proposed to the DSMB for assessment in Stage 2.

In Cohort 2, both non-compartmental and population PK analyses will be performed using the plasma concentration data generated. Population means and variances of PK parameters for DTG will be estimated using nonlinear mixed-effects regression models (e.g., using NONMEM VII software). Subject covariates will be assessed to explain sources of inter-subject PK variability. Changes in DTG drug exposures and trough concentrations in neonates following multi-doses of DTG during the first 28 days of life will be estimated using the final model.

If necessary, pooling concentration data available in other studies of DTG in children living with HIV, particularly the IMPAACT P1093, 2019, 2036 and/or ODYSSEY trials, will be considered for model development with agreement from the corresponding study teams.

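### One missed 1 h or 2 h sample ends Stage 1 PK sampling and replaces an already dosed neonate, so the later samples behind C24, AUC and CL/F are never drawn

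*Protocol*

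**What the plan says.** Section 9.4 gives two triggers that end PK sampling in Cohorts 1A and 1B. One is emesis within 30 minutes with a dose judged not fully retained. The other is "If either the first or second PK sample at 1 or 2 hours post-dose are missed". The consequence is stated as "If the PK sampling is terminated the child will continue in the study for safety assessment but repeat PK sampling will not be performed", and then "Participants who do not complete the PK visit in Stage 1 will be replaced". No reason is given for the missed-sample trigger.

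The planned draws are, for Cohort 1A (Section 9.2.1.1), "Following an observed dose, blood will be drawn at 1, 2, 3, 4, 6 (PK Visit 1a) and 24-30-hours (PK Visit 1b) post-dose", and for Cohort 1B (Section 9.2.2.1), "Blood will be drawn pre-dose, and then following an observed dose, at 1, 2, 4, and 6 (PK Visit 1a), and 24-72 hours" post-dose. Each draw is 0.4 mL.

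Three other places bear on the rule:
- Section 12.2.4 computes clearance as dose over AUC0-infinity, with a linear-up log-down trapezoid, and says "Pharmacokinetic modelling and simulation analyses using all Stage 1 PK data will be performed" to choose the Cohort 2 schedule.
- Sections 11.4 and 11.4.1 select that schedule on C24 (above 0.67 µg/mL) and Cmax (below 17.0 µg/mL).
- Section 12.2.1 admits to the PK population any treated infant with at least one PK assessment.

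**The concern.** When the missed-sample trigger fires, the neonate has already taken and retained the 5 mg dose. Almost nothing has been collected by then. In Cohort 1A it is no sample at all (1 h missed) or the 1 h sample alone (2 h missed). In Cohort 1B it is the pre-dose sample, with or without the 1 h sample. The draws that are cancelled are the ones that describe elimination, and the last of them largely fixes the terminal slope.

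The infant has carried the exposure, contributes nothing on C24, AUC0-infinity or CL/F, and is replaced by a further newborn. Section 13.6 says Stage 1 infants will likely have no direct benefit from the dose. With 8 infants per cohort, each profile counts.

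**Working it through.** The protocol gives no figure for this rule, so there is none to reproduce. The question is how much one missing early sample costs if the other draws go ahead.

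**Inputs from the protocol.** Sampling times as above. Half-life: Section 8.2.1 reports neonatal washout "with a median elimination half-life of 32.8 hours compared to 12-14 hours in children and adults". Tmax 2 to 3 h (Section 8.1). AUC method from Section 12.2.4.

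**Assumptions.** One-compartment oral curve; half-life 14 to 48 h; ka 0.5 to 2/h; no assay noise; zero pre-dose level; terminal slope from the last two samples.

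**Formula.** With dose/V set to 1 and k = ln 2 / half-life, C(t) = ka/(ka − k) × [exp(−kt) − exp(−ka·t)].

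**Worst corner of the grid, half-life 14 h and ka 2/h (Tmax 1.9 h), Cohort 1B, last sample at 48 h.** C at 1, 2, 4, 6 and 48 h is 0.8371, 0.9099, 0.8408, 0.7619 and 0.0952. AUC0-infinity from the full profile is 20.03.
- 1 h missing: the area from 0 to 2 h changes from 0.4186 + 0.8735 = 1.2921 to 0.9099. The loss of 0.3822 is 1.9% of 20.03. Observed Cmax stays 0.9099.
- 2 h missing: the area from 1 to 4 h changes from 0.8735 + 1.7498 = 2.6233 to 3 × (0.8371 + 0.8408)/2 = 2.5169. The loss of 0.1064 is 0.5%. Observed Cmax becomes 0.8408, and 0.8408/0.9099 = 0.924, a fall of 7.6%.
- 2 h missing in Cohort 1A: the 3 h sample is 0.8813, and 0.8813/0.9099 = 0.969, a fall of about 3%.

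**Largest change over the whole grid**

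| Missing | AUC0-infinity, 1A | AUC0-infinity, 1B | Observed Cmax, 1A | Observed Cmax, 1B |
|---|---|---|---|---|
| 1 h only | 1.9% | 1.9% | 0% | 0% |
| 2 h only | 0.4% | 0.9% | about 3% | 7.6% |
| both | 4.3% | 6.8% | about 3% | 7.6% |

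A separate grid defined by Tmax 1.5 to 4 h gives, for one missing sample, at most 2.2% for AUC0-infinity and 7.0% for Cmax. For both missing it gives 7.2% and 9.0%.

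One affected infant among 8 moves the cohort geometric mean by about ln(0.981)/8 = −0.2% for AUC0-infinity and ln(0.924)/8 = −1.0% for Cmax. Section 12.1 plans for a between-infant CV of 50% in CL/F.

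**With noise.** Simulated infants had an assumed CV of 50% for CL, 30% for V and 70% for ka, and 15% residual error. At half-life 32.8 h and Tmax 2 h in Cohort 1B, the root mean square error of log AUC0-infinity against truth is 0.333 with all samples, 0.337 without 1 h and 0.334 without 2 h. Across the Cohort 1B scenarios, 13% to 20% of infants lacking the 2 h sample had an observed Cmax more than 10% below their full-profile value. Error against the true Cmax did not rise, partly because the maximum of several noisy samples overstates the peak.

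**Extra neonates dosed.** If each early sample is missed independently with probability p, sampling stops with probability q = 1 − (1 − p)². The expected number of extra infants dosed to complete 16 is 16q/(1 − q). For p = 2%, 5% and 10%, q is 4%, 10% and 19%, giving 0.7, 1.7 and 3.8. These rates are assumptions.

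**The case against.** The best defence is Cmax. It is a primary endpoint, one of the two selection criteria, and the quantity limited because of bilirubin displacement. Drug levels peak at 2 to 3 h, and in Cohort 1B a missed 2 h sample leaves nothing between 1 h and 4 h. Requiring both early samples therefore has a visible rationale. That stands, and it is a good reason to treat such an infant's Cmax with care. It is no reason to cancel the later draws, which cannot restore Cmax and are what the other measures need.

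Continuing also means more sampling from that infant: after a missed 1 h sample, five draws (2.0 mL) in 1A or four (1.6 mL) in 1B. These draws are already planned, and a replacement undergoes a full set.

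Several stronger readings are tempting but unsupported:
- That collected data are thrown away. The rule stops collection; samples already drawn are not excluded by the PK population definition.
- That CL/F sets the Cohort 2 schedule. Sections 11.4.1 and 12.2.4 select on C24 and Cmax.
- That Cohort 2 contradicts Stage 1. For Cohort 2, the clause "Once started, the PK blood sampling at Visit 2 will be terminated if" is followed by emesis alone. But Cohort 2 also replaces infants with incomplete Visit 2 sampling, can reschedule the visit, and has further samples at Entry and Visit 5. The difference can follow from the design.
- That a mixed-effects model is specified for Stage 1. Section 12.2.4 names that method under Cohort 2; for Stage 1 it speaks only of appropriate PK models.

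**Conclusion.** The point holds as a cheap improvement to the design; it is not an error or contradiction in the protocol. With one early sample missing and the rest drawn, AUC0-infinity and hence CL/F change by about 2% or less. Observed Cmax changes by 0% (1 h missing) or by up to about 3% in 1A and 8% in 1B (2 h missing). These are noise-free figures under a one-compartment model over the assumed ranges. They are not bounds for an individual infant, where noise can make the Cmax shift larger. Under the present rule that infant supplies none of the later information and another neonate is dosed. How often this would happen cannot be derived from the protocol; 0.7 to 3.8 extra neonates over Stage 1 holds only if 2% to 10% of early samples are missed. A trigger that requires both early samples to be missing would be easier to defend, since the AUC loss is then about 7% in Cohort 1B.

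**What to change.** Two sentences in Section 9.4 need to change together.

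1. Amend the missed-sample bullet so that missing only one of the 1 h and 2 h samples does not end sampling. Take the remaining planned draws and use them for AUC, C24, CL/F and the Stage 1 modelling. Flag the infant in the Cmax and Tmax summary, or present that summary with and without the infant.
2. Amend the replacement sentence to match. For missed samples, replacement would apply when both early samples are missed or when AUC0-infinity and CL/F cannot be estimated. Changing the bullet alone is not enough, because an infant lacking one sample could still be read as not having completed the PK visit. The emesis trigger and its consequence are unaffected.

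Cost: up to five (1A) or four (1B) already planned 0.4 mL draws in an infant whose observed Cmax is less certain, and possibly one fewer infant in the Cmax summary.
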